1. INTRODUCTION

Obesity is a significant public health concern. Nearly two-third of US adults are overweight or obese (body mass index [BMI] ≥ 25 and ≥ 30 kg/m², respectively).¹ It is well known that excess body weight is associated with increased risk for a number of chronic conditions including diabetes, heart disease, and some cancers including colorectal cancer (CRC).

Effective dietary strategies are essential to address the issues of obesity and related metabolic disorders. Diet composition is one factor that could influence dietary energy intake. For example, diets that are high in fiber require more chewing and a greater volume is consumed at a given energy intake (kcal/g). These factors could lead to earlier termination of eating and increased satiation. In addition, fiber-rich diets may impact physiological mechanisms important for weight control including hormone release and gastric emptying.^{2,3}

Epidemiologic research has linked higher legume consumption with reduced risk for obesity² and in some studies, with reduced risk for CRC and the precursor lesions, adenomatous polyps.⁴ In previous research that targeted men at increased risk for CRC we observed that a high-legume diet provided under conditions of weight maintenance favorably influenced biomarkers of inflammation, lipid levels, and gut hormone concentrations.⁵⁻⁹ In the same study, during a 4-week ancillary diet period where participants consumed the full legume diet entrée but with side dishes ad libitum and were allowed to lose weight, the high-legume diet facilitated weight loss.⁸ Participants consumed less total energy (-770 kcal/d below requirements for weight maintenance), lost weight (-4.0 kg; -4.4%) and serum lipid and gut hormone concentrations and biomarkers of insulin sensitivity (plasma glucose: -5.7%; insulin: -15.8%; serum C-peptide: -17.4%) and inflammation (serum CRP: -20.2) all improved significantly. This sub-study was conducted after an intensive 12 week randomized controlled crossover feeding trial but the sub-study itself was not randomized and controlled. We did not have the resources needed to conduct a feeding response time-course experiment or to explore other novel mechanisms through which legumes may facilitate weight loss (e.g. appetite-regulating hormones, gastric emptying and transit time). In addition, the provision of all of the diet components may have played a role in controlling intake and promoting weight loss.

The goal of the currently proposed study is to build upon our previous findings by conducting a randomized controlled feeding pilot study within a more diverse population also at high risk for CRC to evaluate whether a high-legume diet will result in increased satiety and in turn will facilitate reduced energy intake and weight loss compared to a control diet provided under similar conditions. In addition, we will explore potential beneficial effects of the high-legume diet on gastric emptying and circulating levels of appetite-regulating hormones and other biomarkers. Dietary behaviors that are even moderately more satiating over time have the potential to enhance weight loss and could lead to a significant public health impact among populations at high risk for CRC and other chronic diseases.

1.1. Study Objectives

This pilot randomized trial will evaluate the effects of diet composition, comparing a legume-rich diet and a control diet, on weight loss over the course of eight weeks. The primary outcome is weight loss. Secondary objectives will compare the effects of the two diets on total energy intake, biomarkers related to appetite regulation and blood glucose control and in exploratory

analyses will assess other aspects related to weight loss (e.g., effects on gastrointestinal emptying and transit time and on gut microbiota).

1.1.1. Primary Objectives

1. Evaluate the effects of a high-legume diet compared to a control diet with a similar macronutrient profile on weight loss in a randomized controlled feeding study conducted over eight weeks.

1.1.2. Secondary Objectives

1. Assess whether the legume diet reduces the average daily dietary energy intake of participants compared to a controlled diet.
2. Compare satiety of the high-legume diet to the control diet using self-reported satiety questionnaires.
3. Assess the effects of the two diet treatments on fasting levels of C-reactive protein (CRP, a marker of inflammation) and total cholesterol level.
4. Evaluate the effects of the aforementioned diet treatments on markers of appetite regulation (cholecystikinin – CCK) and insulin resistance (insulin, glucose) in a meal response time course experiment.
5. Compare the effects of the high-legume and control diets on gastric emptying time and gut transit time.
6. Evaluate diet-related changes in fecal biomarkers associated with CRC risk.

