2.2.1. Strategies to Recruit and Enroll Participants

Subjects eligible according to a phone interview will be invited to one of the study sites. On this visit, after receiving informed consent, the participant's height, weight, and blood pressure will be checked. All eligible consented participants will be asked to visit the Emory ACTSI site to assess their resting metabolic rate (RMR) to be used to plan meals that will facilitate a weight loss of 1-2 pounds per week (energy deficit ~500-1000 kcal/day). Once their individualized diet plan is developed participants will all undergo a one-week run-in of diet similar to the control diet. The run-in helps to standardize conditions before the baseline biomarker collection and provides some confidence in the participants' ability to adhere to the study protocol.

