3.1.1. Timing of Biological Specimen Collection

At randomization, after a one week run-in period, the baseline blood and fecal samples will be collected. These same specimens will be also collected at the end of the study period, after 8 weeks. All biomarker collections will take place at the Emory ACTSI site.

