4.1.2 Body Composition

Body composition will be assessed using dual energy X-ray absorptiometry (DXA) in the ACTSI at Emory University. This method uses a whole-body scanner to measure total body composition and fat content with a high degree of precision. It is safe and noninvasive with little burden to the individual. Data from the DXA scans will be used to assess longitudinal changes in body fat that accompany weight loss. This data will also allow examination of changes in fat distribution at defined regions in the body.

4.1.3. 24 Hour Diet Recall

Subjects will be asked by a trained study staff member to recall their food and beverage intake during the previous 24 hour period or the preceding day. During the week prior to randomization, two unannounced telephone 24 hour recall interviews will be conducted, one during a weekday and one on a weekend. This will be repeated again during the second week after randomization, and again during the 7th week of randomization. The interview will follow a four-stage, multiple-pass interview technique and be conducted over the phone using Nutrient Data Systems for Research (NDSR), the state of the art diet assessment and nutrient analysis

program for research. NDSR estimates total energy, macro- and micro-nutrient intake and captures intake for the entire day, specific meals, dietary patterns, or individual foods.

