Within-subject changes in end-points will be compared by paired t-test; comparisons between treatment groups by two-sample t-tests. For the time course experiments, because of the large expected individual variations in fasting levels of metabolic and appetite hormones, we intend to compute the change from baseline at each time point for each individual for all of the variables and subsequently comparing the area under the curve results⁵⁵. All data will be presented as means \pm SEM; the probability level at which differences will be considered significant will be $P < 0.05$. All analyses will be performed using the most recent version of SAS (SAS Institute, Cary, NC).

Timeline

	Mo. 1	Mo. 2	Mo. 3	Mo. 4	Mo. 5	Mo. 6	Mo. 7	Mo. 8	Mo. 9	Mo. 10	Mo. 11	Mo. 12
IRB Approval, set up	X	X										
Recruiting			X	X	X	X	X	X				
Follow-up				X	X	X	X	X	X	X		
Biomarker Analysis									X	X	X	X
Statistical Analysis											X	X
Manuscript Preparation											X	X
Report to Funding Agency												X
Draft of Subsequent R01												X

REFERENCES

1. National Center for Health Statistics (NCHS). National Health and Nutrition Examination Survey Data. 2005-2006. *US Dept. of Health and Human Services, Centers for Disease Control and Prevention*. 2007; Washington, DC.

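### Energy intake (secondary objective 1) has only an unadjusted two-sample t-test, leaving two baseline predictors already collected, RMR and recalled intake, unused, so precision is lost.

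*Combined protocol and SAP*

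**What the plan says.** Section 1.1.2 lists as its first secondary objective: "Assess whether the legume diet reduces the average daily dietary energy intake of participants compared to a controlled diet". No scaling to body size or energy requirement is named.

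Section 4.2 gives paired t-tests for within-subject changes and "comparisons between treatment groups by two-sample t-tests". It does not say whether the between-group test for energy intake uses follow-up values or changes. It says BMI will be considered as a confounder but gives no model, and it links this to the target population and possible stratification of a full-scale trial.

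Two predictors of intake are available before randomisation:

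- **RMR.** Section 2.2.1 sends all eligible consented men to "assess their resting metabolic rate (RMR) to be used to plan meals that will facilitate a weight loss of 1-2 pounds per week". This comes before the run-in, and section 3.1.1 places randomisation after it: "At randomization, after a one week run-in period, the baseline blood and fecal samples will be collected". Meal planning is the only stated use of RMR.
- **Baseline recalls.** Section 4.1.3 says: "During the week prior to randomization, two unannounced telephone 24 hour recall interviews will be conducted, one during a weekday and one on a weekend". For follow-up it says: "This will be repeated again during the second week after randomization, and again during the 7th week of randomization". That gives two baseline and four follow-up recall days per man.

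**The concern.** Each man's diet plan is built on his own RMR, and eligible BMI runs from 25 to 40 kg/m², so part of the spread in daily energy intake between men reflects body size and not diet. With 7 men per arm, chance can leave the arms unequal in mean energy requirement by an amount comparable with a plausible diet effect. An unadjusted test carries all of that variation in its standard error.

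Two things are at stake. Intake is the route by which the plan expects legumes to reduce weight, so a needlessly wide interval weakens what the pilot can say about mechanism. Section 4.2 also wants the secondary outcomes to inform the size of a full-scale trial, and an unadjusted SD would carry forward variance that a baseline measure could remove.

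**Working it through.** **The plan's own figure.** Section 4.2 sizes only weight loss: difference 1.25 kg, SD 0.7 kg, 80% power. Two-sided normal approximation: n per arm = 2 × [0.7 × (1.960 + 0.842) / 1.25]² = 4.92, rounded up to 5, so the stated 10 is reproduced. The plan then recruits 7 per arm. It gives no SD, effect size or power for energy intake.

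**Intake difference implied by 1.25 kg.** Section 2.2.1 equates about 500 kcal/day with 1 lb/week. Over 8 weeks: 1.25 × 2.2046 / 8 × 500 = 172 kcal/day. As a sensitivity check, the Introduction's earlier sub-study (770 kcal/day, 4 weeks, 4.0 kg) implies 770 × 28 / 4.0 = 5390 kcal/kg, which gives 1.25 × 5390 / 56 = 120 kcal/day.

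**Chance difference in mean requirement, 7 per arm.** SE = SD × √(2/7). The SDs are assumptions.

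| Assumed SD of requirement (kcal/day) | SE | P(exceeds 172) | P(exceeds 120) |
|---|---|---|---|
| 200 | 107 | 11% | 26% |
| 300 | 160 | 28% | 45% |
| 400 | 214 | 42% | 57% |

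Probabilities are for either direction.

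**What RMR adjustment gains.** Further assumptions: RMR explains R² = 50-80% of requirement variance; other between-man SD is 150-250 kcal/day; day-to-day SD is 500-700 kcal/day, averaged over four independent follow-up days.

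- Unadjusted variance per man: V = SD_req² + SD_other² + SD_day²/4.
- Residual variance after adjustment: A = V − R² × SD_req².
- Small-sample cost: estimating one slope with 12 within-arm degrees of freedom inflates the variance of the contrast by 1/(12 − 2) = 10% on average.
- Net cut = 1 − 1.1 × A/V.

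| SD_req / SD_other / SD_day / R² | V | A | Cut before cost | Net cut |
|---|---|---|---|---|
| 200 / 250 / 700 / 0.5 (least favourable) | 225,000 | 205,000 | 9% | 0% |
| 300 / 200 / 600 / 0.5 (midpoint) | 220,000 | 175,000 | 20% | 13% |
| 300 / 200 / 600 / 0.8 (midpoint) | 220,000 | 148,000 | 33% | 26% |
| 400 / 150 / 500 / 0.8 (most favourable) | 245,000 | 117,000 | 52% | 47% |

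Simulation agrees to within about a percentage point (47-48% in the last row).

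**Baseline recalled intake as the covariate.** If the stable part S = SD_req² + SD_other² is the same before and after randomisation, residual variance is V − S²/(S + SD_day²/2). At the midpoint, S = 130,000 and the residual is 220,000 − 130,000²/310,000 = 165,484. The net cut is 1 − 1.1 × 165,484/220,000 = 17%, inside the 13-26% range for RMR.

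**Change from baseline.** The stable part cancels, but two-day baseline noise is added: variance = SD_day²/2 + SD_day²/4. At the midpoint this is 270,000, against 220,000 for follow-up values alone.

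**Power for 172 kcal/day** (noncentral t, two-sided 5%), over low, middle and high values of each assumption: about 8-13% unadjusted (12 df) and 8-15% RMR-adjusted (11 df, with the 10% cost).

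**The case against.** The strongest reply is that the plan never commits to comparing unscaled follow-up intake. The sentence that names the t-tests opens with within-subject changes, and baseline recalls exist, so a comparison of changes is a fair reading. It would cancel each man's stable body-size component. BMI is also named. This stands to the extent that a reader who infers a raw kcal/day comparison is inferring it from silence. It does not rescue the plan: under the midpoint assumptions a change score is noisier than the follow-up mean, because it rests on only two baseline days, and a confounder without a model is not an analysis.

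A reader might also infer that chance imbalance would bias or swamp the diet effect. The documents do not support this. Under randomisation the imbalance is already reflected in the t-test's standard error, and its size rests on SDs the plan does not give. Against an effect near the 770 kcal/day of the earlier sub-study it would be negligible (probability below 0.1%), although that figure is not a between-arm difference.

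Nor do the documents show that the plan abandoned an established scale. The 770 kcal/day shortfall comes from a sub-study that was not randomised or controlled and so needed an outside reference; here the control arm supplies one.

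Finally, this is a secondary objective of a 14-man pilot with no power claim for intake, and at the unfavourable end of the assumptions adjustment gains nothing. That is fair, and it limits the weight of the point.

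**Conclusion.** The point holds as a loss of precision and an under-specified analysis. For secondary objective 1 the plan leaves open follow-up or change, gives no model for BMI, and makes no stated use of RMR or baseline recalls in the between-arm comparison.

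With a requirement SD of 200-400 kcal/day, chance differences in mean requirement exceed the implied 172 kcal/day target with probability 11-42%. The net variance reduction from RMR adjustment runs from about zero to 47-48%, and is 13-26% at midpoints; baseline-intake adjustment performs similarly. All of these rest on assumed SDs and an assumed R². Low power for 172 kcal/day persists either way, so the case for the change is a tighter estimate and a more useful planning SD. It is worth making because it uses data already collected, but it does not threaten the trial's primary conclusion.

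**What to change.** In section 4.2, for secondary objective 1, replace the two-sample t-test with a linear model of mean recalled energy intake over weeks 2 and 7 on diet arm plus one baseline covariate. Name that covariate before outcome data are seen: measured RMR, or the mean of the two pre-randomisation recalls. RMR is a measurement and not a self-report. The recalls measure the outcome itself, but fall in the run-in week on a control-like diet. Either is valid because both precede randomisation. Report the adjusted difference with its 95% CI, and the residual SD for planning the full-scale trial.

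Do not add a report of intake as a shortfall below requirement, because the plan gives no conversion from RMR to total requirement.

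The cost is analysis wording, one degree of freedom (12 to 11), and about 10% inflation of the contrast's variance if the covariate turns out to be uninformative. No new data are needed.

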1.2. Background and Rationale

1.2.1. Scope of the problem

Colorectal carcinoma (CRC) is the second leading cause of cancer death in the U.S.¹⁰ Adiposity is a well-known risk factor for CRC and for colorectal adenomatous polyps¹¹, recognized as precursor lesions for the majority of CRCs¹². A significant body of literature suggests that weight and body fatness are positively associated with increased risk for adenoma incidence. More recently investigators have shown that obesity and body fatness are linked with recurrence for colorectal adenomas, particularly among men.¹³ The influence of weight change, particularly weight loss, on risk factors for CRC and adenomatous polyps has been examined in only relatively few studies.^{14,15} A three-year multicenter trial to prospectively address this question is in progress.^{16,17}

1.2.2. Insulin resistance (IR) and colon cancer mechanisms

Insulin resistance, the impairment to the biological response of insulin action, is characterized by compensatory hyperinsulinemia and increased risk for Type-II diabetes (DM).¹⁸ Obesity is a well-known risk factor for insulin resistance and DM. A number of epidemiologic studies have provided convincing evidence for an association between DM and CRC.¹⁹⁻²¹ Exposure to elevated insulin, glucose, and triglycerides could affect growth, development, and homeostasis of colonic cells.^{22,23} Recently, Komminou and colleagues reviewed the mechanistic associations between insulin resistance and CRC, as seen in **Figure 1**.²⁴ Inflammation and cytokine production such as TNF- α , are thought to promote insulin resistance,²³ increase IFG-1, and activate I κ B kinase β (IKK β), an upstream activator of NF- κ B which leads to increased proliferation and decreased differentiation and apoptosis.²⁴

[figure not shown]

Figure 1. Mechanistic association between insulin resistance and colon cancer

1.2.3. Inflammation, insulin resistance and CRC

C-reactive protein (CRP), an acute phase protein, is thought to be a sensitive and particularly stable marker for sub-clinical inflammation. Cytokines, mainly interleukin-6 (IL-6) and tumor necrosis factor (TNF- α) may exert major stimulatory effects on the hepatic synthesis of acute-phase proteins.²⁵ Elevated levels of CRP are commonly found among overweight and obese individuals and are known to predict the development of insulin resistance²⁶⁻³⁰ and type-II diabetes.³¹⁻³³ Inflammation creates a microenvironment that encourages neoplastic transformations and potentiates the progression of cancer. In a recent cohort study³⁴ plasma CRP concentrations were higher among CRC cases than controls (median CRP, 2.44 vs. 1.94 mg/L; $P = .01$) and risk of CRC was higher in persons in the highest quartile of CRP (OR= 2.55; 95% CI, 1.34-4.88; P for trend =.002). In our previous feeding study we demonstrated that CRP levels decreased by over 20% in response to a mean weight loss of 4.0 kg in men at high risk for CRC.⁸

1.2.4. Legumes

Despite the fact that at least 58 studies have evaluated the association between legumes and cancer risk,^{35,36} there is no clear pattern of increased or decreased risk. One potential problem in investigating the relationship between legume intake and CRC is the low intake of legumes in economically developed countries that have a higher CRC incidence.

Intake of legumes provides benefits in reducing risk for diabetes and in diabetes management. Pulses (dry beans) are high in fiber and have a very low glycemic index (GI)³⁷ indicating that after eating pulses, the blood glucose increase is much less than with most polysaccharide-rich foods. Several studies suggest that the intake of pulses offers important benefits for the management of diabetes.³⁸⁻⁴¹ Legumes have also been shown to increase satiety compared to legume-free meals with the same energy content, and randomized trials of legume consumption on weight loss have been generally positive, though energy restriction appears necessary.²

1.2.5. Polyp Prevention Trial (PPT) Data

The strongest dietary association in the PPT cohort was an inverse association between legume intake and advanced adenomas. Those in the highest quartile of average dry bean intake had a

significant reduction in their odds ratio for recurrence of advanced polyps (OR=0.30 95% CI; 0.15-0.60). For males, increased legume intake was also associated with a reduced odds ratio for any adenoma recurrence (OR=0.69 95% CI; 0.48-0.99)⁴. The intervention arm, who consumed more legumes overall, also lost significantly more weight than the control arm,⁴² supporting the hypothesis that a high fiber diet may help with weight management.

1.2.6. Satiety

A high fiber diet increases the volume of food compared to the number of calories consumed (i.e., decreases energy density – ED kcal/g), which creates a greater feeling of gastric fullness for fewer calories.⁴³ Increased fiber content prolongs the postprandial presence of intestinally derived lipoproteins and augments the release of cholecystokinin (CCK), a major gut peptide and a potent satiety signal involved in meal termination.⁴⁴ Several controlled feeding studies with high legume diets have shown increases in CCK.^{45,46} The working hypothesis is that continued consumption of a high-legume, high-fiber diet will result in changes in circulating levels of CCK and related biomarkers measured post-prandially.

1.2.7. Gut Microbiome

A high fiber diet has been known to alter the gut microbiome of individuals provided the duration of the intervention is long enough. Certain intestinal microbiota have been associated with increased or decreased levels of inflammation and obesity. Fiber intervention trials in both human and animal models have shown a decrease in inflammatory response with increasing fiber.⁴⁷ It is unclear whether this effect is at least partially the result of changing gut microbiome composition or if it is a side effect of the fiber-inflammation relationship.

1.2.8. Gastric emptying and GI transit time

The addition of a high-fiber ingredient to a low fat meal can help delay gastric emptying and delay the onset of hunger.⁴⁸ The addition of fiber to a meal can help modulate hunger signaling and therefore may be an important component in weight loss.⁴⁹

2. ELIGIBILITY ASSESSMENT AND ENROLLMENT

We intend to test whether a high-legume intervention will result in increased satiety and in turn will facilitate reduced energy intake and weight loss compared to a control diet provided under similar conditions. We will recruit men at increased risk for colorectal cancer (see below) at two locations (1) Emory University ACTSI and (2) The Morehouse School of Medicine Medical Clinical Research Center Bionutrition Core Center (affiliated with the ACTSI) and surrounding areas. Participants will be recruited through targeted advertisements and (if approved) through targeted mailings with the assistance of local gastroenterologists serving these populations. These recruitment strategies were successfully used in our previous feeding trial which included 65 high risk men.

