3.1.2 Dietary Intervention Administration

A menu cycle will be developed with a standard set of legumes of the *Phaseolus vulgaris* species, such as navy beans, pinto beans, and kidney beans in order to limit nutrient and phytochemical differences in the legume-intervention diet. The diet will contain approximately 250g of legumes per day (~1 ½ cups cooked) provided in two pre-portioned single serving entrees (i.e. ~125g each). This level will add approximately 20 grams of total dietary fiber and 8 grams of soluble fiber per day. Adding 1 ½ cups of legumes would double the dietary fiber content of the typical American diet. The intervention diet treatment will consist of two legume-enriched pre-portioned meal entrees per day with other meal components being provided by the study participants. The control group will also receive two pre-portioned meal replacement entrees, with the other meal components provided by the study participants. All entrees will be prepared, pre-portioned and frozen at the Morehouse site and transported to the Emory site as needed. Frozen entrees will be picked up by participants weekly at the respective study sites and any uneaten entrees returned the following week and recorded. Weights will also be measured weekly at these visits. For both groups, guidance will be provided by study personnel for the meal components which are self-selected to meet participants' diet plans. Study personnel include three registered dietitians (the PI, a Co-I, and an ACTSI RD) to provide dietary guidance which will be supplemented with individualized written materials. During the first 1-2 weeks of the participants' diet treatment the study coordinator will contact them regularly to answer any questions and to provide support and encourage adherence. The consumption of ad libitum "sides" contributing to total energy intake is not controlled by the study to enable us to evaluate the role of legumes in promoting satiety and control of self-selected total food intake.

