4.2. Statistical Considerations

The main endpoint of interest in this study is weight loss. There are several proposed mechanisms by which legumes are thought to promote weight loss, many of which have not been tested in a controlled setting. Due to new technology, we are now able to examine one of these proposed mechanisms—colon transit time, allowing us to directly observe a legume diet's physiologic effect. Previous studies of legume-heavy diets have shown indications that the particular type of fiber specific to legumes may increase satiety and slow gastric emptying significantly, leading patients to consume fewer calories per day, thereby promoting weight loss without intensive intervention from the study staff. Thus, we do expect to have differences in energy intake between groups. The analyses will follow the intent-to-treat principle. BMI will certainly be considered as a possible confounder. Since this is a pilot trial, doing so will be important to determine the appropriate target population for a full-scale trial and whether randomization in that protocol should be stratified by BMI. Secondary outcomes, including both the satiety hormones and glucose are expected to rise quickly in response to the test meal and then decline over the course of the next few hours as gastric emptying occurs.

In the Legume Inflammation Feeding Experiment full-feeding study, participants averaged -3.9 ± 0.4 kg over the course of four weeks⁸. Ten participants (five individuals per treatment arm) would be sufficient to detect a difference of just 1.25kg (we expect > 1 kg) in weight loss, with 80% power, assuming a standard deviation for each groups' weight loss that is slightly higher (± 0.7 kg) than seen in our prior study⁸. To account for the potential small dropout rate, we will recruit a total of 14 patients (7 per treatment arm). There are multiple secondary outcomes that we are interested in determining the appropriate sample size for when we run a full-scale study. Some of these outcomes are novel, so we are exploring the feasibility of pursuing them in a full scale study.

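### The plan recruits at two sites, but the readable text does not allocate within site and the stated t-test omits site, which leaves a 14-man trial open to chance site imbalance and lost precision.

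*Combined protocol and SAP*

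**What the plan says.** Section 2 recruits men "at two locations (1) Emory University ACTSI and (2) The Morehouse School of Medicine Medical Clinical Research Center", using advertisements and, if approved, "targeted mailings with the assistance of local gastroenterologists serving these populations". Section 3.1.2 states that "Frozen entrees will be picked up by participants weekly at the respective study sites" and that "Weights will also be measured weekly at these visits". Weight loss is the primary outcome, so the site handles both the food and the serial weights.

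On allocation, section 4.2 fixes only the totals: "we will recruit a total of 14 patients (7 per treatment arm". No readable passage says how the allocation list is made or balances it by site. Stratification is mentioned once, for BMI, and only as a question for a later full-scale trial.

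On analysis, section 4.2 plans "comparisons between treatment groups by two-sample t-tests". BMI is the one possible confounder named. Site does not appear in the analysis.

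**The concern.** In a two-site trial, allocation is commonly balanced within site and site is kept in the model. Here neither is stated. With only 14 men, the arms can easily end up with different site mixes. If mean weight loss happens to differ by site, an unequal mix moves the diet estimate in the trial actually run. Even with an equal mix, the site difference stays in the residual variance of the t-test and widens the confidence interval. What is at stake is the precision of the primary comparison and how convincingly a single small result can be read.

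**Working it through.** **Inputs from the plan (section 4.2):** target difference 1.25 kg; SD 0.7 kg for each group's weight loss; 80% power; 5 evaluable and 7 recruited per arm; P < 0.05 (two-sided assumed).

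**Assumptions, because the documents give no figure:** the split of the 14 men by site (2/12 to 7/7 tried) and the site gap in mean loss (0 to 1.5 kg tried).

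**1. The plan's own figure.** n per arm = 2(1.960 + 0.842)² × (0.7/1.25)² = 2 × 7.85 × 0.3136 = 4.92, so 5. This reproduces the stated number by the normal approximation. Exact two-sided t-test power is 69.7% at 5 per arm and 86.5% at 7 per arm.

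**2. How often the site mix is uneven.** Take an unstratified 7:7 allocation and 7 men per site. P(4:3 or 3:4) = 2 × 35 × 35 / 3432 = 0.714, so P(5:2 or worse) = 0.286. For other splits, the chance that the two arms' site shares differ by 40 percentage points or more is:

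| Smaller site | 2 | 3 | 4 | 5 | 6 | 7 |
|---|---|---|---|---|---|---|
| Chance | 0% | 19.2% | 7.0% | 26.6% | 10.3% | 28.6% |

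**3. Effect in one realised trial.** Shift = difference in site share × site gap. At 5:2 with a 1 kg gap, (5/7 − 2/7) × 1 = 0.43 kg, and 0.43/1.25 = 34% of the target. Given that mix and a within-site SD of 0.7 kg, simulation gives a false-positive rate of about 9.6%. Power for 1.25 kg is about 36% or 95%, depending on which arm the imbalance favours.

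**4. Effect averaged over allocations (7/7 split).** The mean estimate is 0.00 kg under no effect and 1.25 kg under the target effect. The t-test's type I error is about 5.1% at every gap from 0 to 1.5 kg. So there is no bias on average and no inflation of the overall error rate.

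**5. Power at 7 per arm with a 1 kg gap.** The result depends on what 0.7 kg describes. With share p at one site and gap D, whole-arm variance = within-site variance + p(1 − p)D².
- If 0.7 kg is the within-site SD, the arm SD at 7/7 is √(0.49 + 0.25) = 0.86 kg.
- If 0.7 kg is the whole-arm SD, the within-site SD is √(0.49 − 0.25) = 0.49 kg at 7/7, and √(0.49 − 0.122) = 0.61 kg at 2/12.

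| 0.7 kg is | Planned t-test | Within-site allocation + site term |
|---|---|---|
| within-site SD | about 69% (7/7) to 78% (2/12) | about 85–86% |
| whole-arm SD | about 86% | about 99% (7/7) to 93% (2/12) |

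Other gaps at a 7/7 split: with 0.7 kg within site, the t-test has 86%, 82%, 69% and 52% at gaps of 0, 0.5, 1.0 and 1.5 kg, while the fix stays near 85%. With 0.7 kg for the whole arm, the t-test stays at 85–87% for gaps up to 1.0 kg. A 1.5 kg gap is then impossible, because D²/4 ≤ 0.49 gives D ≤ 1.4 kg.

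**6. Price of the fix when there is no gap.** Residual df fall from 12 to 11 and the critical t rises from 2.18 to 2.20. With exact balance, power falls from 86.5% to 86.0%. Across the splits tried, the loss is about 0–2 points at 7 per arm and 2–4 points at 5 per arm. A site term without within-site allocation gives about 82–83% at a 7/7 split (0.7 kg within site), so the allocation contributes as well as the model.

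**The case against.** A reader might infer that the two sites serve different populations with different staff. The documents do not say so. The phrase "within a more diverse population also at high risk for CRC" contrasts this trial with the previous study, not one site with the other. Eligibility criteria are common to all men. Section 3.1.2 describes one group of dietitians, not assigned by site, and "All entrees will be prepared, pre-portioned and frozen at the Morehouse site". Metabolic rate, physical examination, DXA and biomarkers are all at Emory, and section 4.1.1 sets one weighing procedure on a calibrated scale. Section 2.1.1 asks that men can reach either food site, so site may not even be a fixed attribute. This stands: a site effect is possible but undocumented.

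A reader might also infer that omitting site biases the diet effect or invalidates the test. Step 4 shows that it does not. Conditional imbalance applies to any prognostic factor in 14 men, and on average the t-test's standard error already allows for it.

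Nor is a fall in power to 69% or 52% a property of this plan. Section 4.2 words 0.7 kg as each group's SD. Read as the whole-arm SD, the planned t-test keeps about 86% power at a 1 kg gap. That removes the headline loss but not the forgone gain, since the fix would then reach 93–99%.

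Finally, the design figure is not shown and could carry allocation detail. The written analysis would still omit site.

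**Conclusion.** The concern holds in limited form. Two sites, food pick-up and weekly weighing at the respective sites, no within-site allocation in the readable text, and a t-test without site are all on the page. The consequence is chance imbalance in a single small trial and lost precision, not systematic bias or an inflated overall error rate.

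Its size rests on an assumed site gap and site split. At a 1 kg gap and 7 per arm, the fix is worth about 8 to 16 power points if 0.7 kg is the within-site SD, and about 7 to 13 points if it is the whole-arm SD, over splits of 2/12 to 7/7. If the sites do not differ, the fix gains nothing and costs little. It is a worthwhile improvement to the stated method; its absence would not make the trial's result invalid.

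**What to change.** State the allocation method. Fix each man's site at enrolment, and allocate 1:1 in concealed permuted blocks of varying size within each site. Analyse weight loss with a linear model of diet arm plus site in place of the plain two-sample t-test.

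This needs no additional men, visits or data: a two-stratum list and one model term (1 df). The power cost if there is no site gap is given in step 6. Two practical drawbacks remain. Incomplete blocks may leave the arms slightly off 7:7. The last allocation in a short block may be guessed if the arms are known to staff, so whoever enrols men should not hold the list.
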